10.6.7 Venipuncture Procedure

For the required blood collections, the physician, after proper hand washing and restraint of the child, with assistance from study nurses, will locate the vein, clean the area with 70% isopropyl alcohol, allow it to dry, and collect the blood sample into sterile vacuum tube. Parents are free to remain present for the blood collection.

10.6.8 Vaccination Procedure

First, the injection nurses close the "injection cubicle" while the participant and parent remain outside. They open the **allocation group randomization envelope** (see section 10.4.4.3) for that child's dose (green for dose 1, yellow for dose 2, red for "insurance" dose 3). One injection nurse then shows the card to the other to confirm the dosage and method. Following the details described in section 10.4.2.3 above, the nurse duly prepares the syringe or jet injector cartridge, covers its tip to maintain cleanliness, and sets it down upon a clean surface and covers it.

The child is then brought into the "injection cubicle" and the parents are requested to remain outside. The **INF** vaccine is administered in the dose and route (ID or IM) specified by the randomization card into the anterolateral portion of the left thigh for children less than 12 months of age, or to the left deltoid muscle for children 12 months and older.

Immediately after the vaccination, the injection nurse will observe for several seconds the injection site for any wheal or bleb and any drops of blood or clear liquid, apply a band-aid, and duly note the information in the CRF, along with the time of injection. The *allocation card* is then destroyed and its pieces disposed into a paper shredder, and any remaining injection supplies or equipment removed from view.

The parent(s) and child are then reunited for holding and consoling (in the waiting area) during the subsequent minimum of 30 minutes of observation before reexamination of the injection site by the injection nurse (to avoid unblinding of the physican investigator from any temporary skin dimpling from the injector flange). During the post-vaccination waiting period, the parent/guardian will receive a final briefing and further training for aspects covered in section 10.6.4 above and reminded when to return next to the study center.

HIRRC/CDC Needle-free Intradermal	Page 94	File: 4785-ID-INF-Prot-Engl-2008Jun24.doc
Influenza Study - CDC-ISO-4785	of 138	2008-Jun-24

At least 30 minutes following vaccination, the injection nurse will note any immediate or early local adverse events and complete the remaining data in parts 7, 11, or 15 of Case Report Form (CRF) ("Medical Exam and $[1^{st}/2^{nd}/3^{rd}]$ Vaccination") and questions 1 through 8 of Parts 8 and 12 of the CRF ("Local Immediate Reactions"). In the event of an unexpected immediate local reaction – such as frank bleeding or laceration – the physician will be notified to institute needed medical care, take a photograph, and make appropriate entries in the adverse event section of the CRF. In all cases, the physician investigator will assess questions 10 through 15 of CRF parts 8 and 12 ("Immediate Systemic Reactions"). The parent and participant will then be discharged from the study center.

10.6.9 Rapid Diagnosis and Virus Culture for Influenza-Like Illness

It is useful to know the strains of Influenza A virus circulating in the community during the study, as well as to know which antibody responses in participants may be the result of infection with wild virus and not induced by the vaccine. Any participants who develop influenza-like illness (ILI) during the course of the study, either during their individual phase of active surveillance, as well as after they have "graduated" from the trial, shall have nasal and pharyngeal specimens collected for immediate rapid diagnosis of influenza A versus B. Simultaneous specimens placed in virus culture transport tubes will be quickly frozen and stored at -70°C. Frozen specimens from participants testing positive for influenza A will be shipped on dry ice to a laboratory for virus culture and typing.

The criteria for defining influenza-like illness that will prompt influenza rapid test and virus culture are listed in **Table 8**.

A. Temperature ≥38.3° C
And
B. 2 or more symptoms of
B1. Cough
B2. Sore throat
B3. Rhinitis or runny nose
B4. General malaise
And
C. No other obvious explanation for the fever
And
D. The symptoms have persisted 4 days or less

Table	8.	Definition	of	"Influenza-l	Like	Illness"
-------	----	------------	----	--------------	------	----------

10.6.10 Specimen Preparation, Labeling, Storage, and Shipping

For use in the study, the "CDC and ATSDR Specimen Packaging, Inventory and Repository" (CASPIR) facility for receiving, processing, and shipping medical

HIRRC/CDC Needle-free Intradermal	Page 95	File: 4785-ID-INF-Prot-Engl-2008Jun24.doc
Influenza Study - CDC-ISO-4785	of 138	2008-Jun-24

specimens (http://www.cdc.gov/od/ads/caspir/), will prepare preprinted sets of peel-off, freezer safe, specimen labels meeting its guidelines. Each label will contain its own unique CASPIR-assigned serial no. and barcode.

10.6.10.1 Serum Specimens

For collection of serum for antibody assay, sets of 12 adjacent labels will also be labeled with identical barcoding and printing of the study designation code + study number + participant identification number, followed by the character "A" to link and identify blood collection tubes and aliquots from the first blood draw on day 0. Similarly, 12 labels for that participant will be printed with "B" to link and identify specimens from the second blood draw on nominal day 28, as well as another 12 labels printed with "C" for the third blood draw on nominal day 56.

Each label within each series of 12 (A, B, and C) will also be numbered and barcoded sequentially with "aliquot-01", "aliquot-02", and so on up to "aliquot-12". The highest aliquot number(s) will be affixed to the appropriate box on the CRF for that blood specimen, and onto other documents as needed.

The 5 mL specimens of whole blood to be collected on day 0, day 28, and day 56 for each participant will be prepared into serum the same day as drawn. The DEI/HIRRC laboratory will divide them into sequential cryovial tubes to be labeled starting with "aliquot-01", "aliquot-02", etc. Each tube will contain only 300 μ L (0.3 mL) volume until the serum is used up or aliquot-08 is reached, which shall contain the remainder of serum available. If less than 600 μ L total serum is available, it should be divided into only two aliquots. Serum should be stored at - 70° C (with emergency power generator backup). Storage as warm as -18° C is acceptable in case of emergency.

At periodic intervals determined by the investigators, one half of the total aliquots from each participant for each draw will be consolidated into a subset for shipment on a Monday or Tuesday only, during non-holiday weeks, by overseas dry-ice air freight service to the CASPIR^g for interim and long-term storage and eventual transshipment to the study assay laboratory (see section 10.6.12). Shipments from the Dominican Republic will be arranged and handled by experienced international medical specimen shipment companies, e.g., OCASA ([contact]), World Courier (http://worldcourier.com/us/indexsz.html) or Quick International (http://www.quickintl.com/).

While the first subset of aliquots is being shipped, the remainder shall remain at HIRRC in case of damage or loss in shipment of the first set. After the first set is received successfully at the specimen storage facility, the remaining aliquots will

^g Shipment delivery address: CDC CASPIR, [name], [contact], [contact], Contact person: [name], [contact].

HIRRC/CDC Needle-free Intradermal	Page 96	File: 4785-ID-INF-Prot-Engl-2008Jun24.doc
Influenza Study - CDC-ISO-4785	of 138	2008-Jun-24

then be shipped. Similar procedures should be followed for phase II specimens, except interim shipments may be made at the discretion of the study investigators. Upon the direction of the U.S. Principal Investigator, CASPIR will transfer specified aliquot(s) to the designated laboratory for serologic assays.

Serum remaining from the study after testing shall be kept in long-term storage by the CASPIR specimen repository and by the testing laboratory. They may be transferred elsewhere upon request by the CDC or HIRRC investigators for additional testing or permanent storage, in accordance with the provisions of the informed consent. Such specimens shall remain the joint property of CDC and HIRRC, and should not be disposed or tested without their mutual consent.

10.6.10.2 Virus Culture Specimens

CASPIR will also prepare sets of 8 duplicate-numbered stickers for use in linking and identifying nasal and pharyngeal specimens collected into virus culture transport tubes and kits for rapid influenza testing. One label from each series will be inserted into the appropriate box on the CRF. These specimens will be collected only when participants develop influenza-like illness, in order to determine which strains of influenza A may be circulating during the study period.

10.6.11 Data Coding, Handling, and Analysis

As detailed in section 10.4.4 above, the blinding codes will be maintained in three secure locations by the independent party and other member(s) of the Data Safety Monitoring Board, as well as kept under seal by the HIRRC hospital director (in the BLUE envelopes, see 10.4.4.4). Codes will not be shared ("broken") with the study investigators (except as described in 10.4.4) until all clinical aspects of the study are completed and missing data obtained, and the serologic assays, performed blind, are completed and results shared.

Case Report Forms, Parent Diary, and other data recording sheets and forms from the study will be duplicated, with the originals kept in the HIRRC and complete copies furnished and maintained for analysis and preservation by the CDC. Data entry and analysis will be performed at CDC, with sharing of programming and data files with HIRRC (and with other parties at the discretion of the principal investigators once blinded laboratory assays are completed and results provided to CDC and HIRRC).

Once a CRF and its related forms are completed, verified, collected, and copied by the Dominican Principal Investigator, no additional information may be added to the originals. Any additions or corrections to the data of the CRF and related forms shall be made by means of the Data Clarification Form (DCF). This form (sections 11.4 and 13) shall be used to track inquiries to the clinical investigators from the sponsor (CDC) about entries in data fields of the Case Report Form, and/or to explain any subsequent changes in the data by the clinical investigators at HIRRC.

10.6.12 Laboratory Assays

10.6.12.1 Serology

Serologic assays for the study will be performed by a facility selected through WHO tender from among qualified research level institutions. For example, invitations will be extended to the Laboratory for Specialized Clinical Studies, Division of Infectious Diseases, Cincinnati Children's Hospital Medical Center, Cincinnati, Ohio, USA, as well as to the National Institute for Biological Standards and Control, Potters Bar, Hertfordshire, UK.

Hemagglutination inhibition assays (HI) against viral strains similar to those included in the vaccine studied will be performed according to current Good Laboratory Practices (cGLP) and standard assay protocol. ^{Palmer1975, Lennette1995} Neutralization and/or other assays, may also be performed as valid indications arise and resources permit.

Subject to agreement for justifiable deviations, specimens will be handled and tested as follows: Upon arrival in the serology laboratory, sera will be stored at - 20°C or colder until analyzed. Specimens will be treated at a dilution of 1:4 with receptor-destroying enzyme (RDE, *Vibrio cholerae* abnormal type 558 strain RDE; Denka Seiken Co., Ogdensburg, N.Y. and Tokyo, Japan, or equivalent) to eliminate nonspecific inhibitors, and then incubated for 16-18 hours in a 37°C H₂O bath. This will be followed by a second incubation for 30 minutes in H₂O bath at 56°C in order to inactivate the RDE.

After RDE inactivation, the HI process proceeds by diluting serum already at 1:4 in serial 2-fold steps (4, 8, 16, 32, 64, 128, 256, 512...) until a final dilution of 1:1024. Each specimen is separately diluted 1:4 and 1:8 for use as serum controls on each plate in which the specimen is tested. In addition to the serum controls, a red blood cell (RBC) control is also included on the plate for each specimen analyzed. At this point, 0.025 mL is transferred to duplicate rows of one test plate for each virus antigen to be analyzed. This yields four specimens per test plate with nine usable test dilutions, two serum controls and one RBC control in each of the duplicate rows.

The prepared, specified virus strain antigens are added to the nine test dilutions of every specimen and 0.025 ml of phosphate-buffered saline (PBS) is added to the serum and RBC controls. Each day assays are performed, the antigen is prepared to contain 4HA units/0.025ml. Virus strain antigens may be supplied from external reference laboratories, or prepared on site by the laboratory.

The antigen-serum mixtures are incubated at room temperature for 30 minutes. Next, 0.050 mL of a 0.5% chicken RBC solution is added to each well. Turkey RBCs may be used if chicken RBCs are not compatible with a specific virus antigen. Upon adding the RBC solution, the plates are incubated for 30 minutes at

HIRRC/CDC Needle-free Intradermal	Page 98	File: 4785-ID-INF-Prot-Engl-2008Jun24.doc
Influenza Study - CDC-ISO-4785	of 138	2008-Jun-24

room temperature, after which they are tilted and read. The titer is the reciprocal of the last dilution that shows complete inhibition of agglutination.

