9.6.4 Research Questions

- Will the investigational study arm of children receiving two doses of 0.1 mL of influenza vaccine administered ID demonstrate *non-inferiority* to the immune responses achieved by the control study arm of children receiving two conventional, full-doses of 0.25 mL administered IM by needle-syringe? (Primary endpoint: proportion of participants achieving inverse titer of ≥40 on hemagglutination inhibition assay for each virus strain in the vaccine.)
- 2. What will be the safety profile of jet-injected, reduced-dose, intradermal influenza vaccination (erythema, induration, limb swelling, bleeding, and other local and systemic reactions) delivered by DCJI using an investigational spacer for ID delivery?
- 3. Will an investigational study arm of children receiving two reduced doses of 0.1 mL of vaccine administered IM by needle-syringe demonstrate *non-inferiority* to the immune responses achieved by the control arm of children receiving conventional, full-dose 0.25 mL administered by the same method in the same target tissue (obviating any need for intradermal delivery to achieve dose sparing)?

10. Investigational Plan

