10.5.1.2 Primary Efficacy Variable

Seroconversion (SC) is the primary efficacy variable. It is defined as the development of an inverse hemagglutination inhibition (HI) titer of \geq 40 on *followup* serum collected one month after the second vaccine dose among initially-seronegative participants (undetectable inverse titer of <8 on *baseline* day 0); OR, for participants with a detectable *baseline* titer, the development of a *followup* HI titer which rises \geq 4-fold. (Usually analyzed as a proportion among participants.)

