10.5.1.3 Secondary Efficacy Variables

Secondary efficacy variables are:

Seroprotection (SP), defined as the development of an inverse HI titer of \geq 40 on *followup* serum collected one month after the second vaccine dose, regardless of evidence of immunity at *baseline*. (Usually analyzed as a proportion among participants.)

Mean geometric increase, defined as the ratio of the geometric mean titers (GMT) of all participants on *followup* HI assay divided by the GMT of HI assay on the same participants at *baseline* (excludes participants with baseline titers lost to followup). (For example, a mean baseline inverse GMT of 18 and followup of 81 would have a mean geometric increase of 4.5.)

Dose 1 seroconversion, defined according to the seroconversion criteria above one month after only the first dose of influenza vaccine, before receiving dose 2.

Dose 1 seroprotection, defined according to the seroprotection criteria above one month after only the first dose of influenza vaccine, before receiving dose 2.

Dose 1 mean geometric increase, defined according to the mean geometric increase calculation above after only the first dose of influenza vaccine, before receiving dose 2.

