10.8 Statistical Methods and Determination of Sample Size

10.8.1 Statistical and Analytical Plans

10.8.1.1 Primary Efficacy Analysis

The primary analysis of efficacy will be comparison of the proportion of participants within each investigational route of administration – ID-JI-0.1 and IM-NS-0.1 – achieving seroconversion one month after the second dose of vaccine to each vaccine strain versus the control needle-syringe full-dose route (IM-NS-0.25). As defined in section 10.5.1.2, the criteria for *seroconversion* to a vaccine strain will be a hemagglutination inhibition (HI) assay titer of 1:40 or greater for those with initial undetectable titers, or an increase of 4-fold or greater from a measurable initial titer to final titer.

Each reduced-dose investigational study arm, ID-JI-0.1 and IM-NS-0.1, will be considered an acceptable alternative method of vaccination if there is no more than a twelve percent decrement in the proportion of participants seroconverting compared to that of the full-dose, IM, needle-syringe control vaccination comparator (IM-NS-0.25) (*non-inferiority* model).^{FDA1998, Chow2002}

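### The default HI dilution series cannot read 40, and the seronegative limit of below 8 does not fit the cut-off of 40, so rates labelled ≥40 are largely read at 64

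*Protocol*

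**What the plan says.** **Assay.** Section 10.6.12.1 describes "diluting serum already at 1:4 in serial 2-fold steps (4, 8, 16, 32, 64, 128, 256, 512", continuing to 1:1024, run in duplicate rows. It counts the wells: "This yields four specimens per test plate with nine usable test dilutions". The reading rule is "The titer is the reciprocal of the last dilution that shows complete inhibition of agglutination". The description is a default: "Subject to agreement for justifiable deviations, specimens will be handled and tested as follows". The synopsis also allows a final dilution beyond 1:1024.

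**Cut-off.** The research questions in 9.6.4 use the "proportion of participants achieving inverse titer of ≥40 on hemagglutination inhibition assay for each virus strain in the vaccine". In 10.5.1.2 a child with an "undetectable inverse titer of <8 on" day 0 must reach 40, and a child with a detectable baseline must show at least a 4-fold rise. In 10.8.1.1 the criterion "will be a hemagglutination inhibition (HI) assay titer of 1:40 or greater for those with initial undetectable titers", with the 4-fold route for any measurable initial titre. Seroprotection in 10.5.1.3 is "defined as the development of an inverse HI titer of" at least 40 whatever the baseline. Section 10.8.1.2 repeats that value and, in item d, sets seroprotection above 70% as one of the criteria to be checked.

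**The concern.** A threshold is applied at the value named only if the assay can read that value. Here the written series skips 40, so a serum whose inhibition ends between 40 and 64 reads 32 and fails, although a series containing 40 would pass it.

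The primary definition has its own fault. The seronegative limit and the required titre do not match, so a child with a lower baseline can need a higher final titre than a child with a higher baseline.

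At stake are the absolute rates: seroconversion among seronegative children, seroprotection after doses 1 and 2, the >70% check, and comparison with rates obtained on another series. A laboratory that follows the written method would not notice anything wrong.

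**Working it through.** **The plan's own sample size.** Inputs from 10.8.2: 0.864 in both arms, margin 0.104, α 0.05, power 0.80, score test. With α one-sided, the score-test formula gives 141 per arm at margin 0.104 and 142 at 0.12 × 0.864 = 0.10368. Normal-approximation power at 142 is 0.804. The stated 142 is reproduced and is not in question.

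**Readable titres.** 4 × 2^k for k = 0 to 8 gives 4, 8, 16, 32, 64, 128, 256, 512, 1024. That is nine values, matching the nine test dilutions in 10.6.12.1, so 4 is a test dilution and 40 is not.

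**Effective cut-off.** The smallest readable value of at least 40 is 64. Distance above the label: log2(64/40) = 0.68 two-fold steps.

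**Duplicates.** 32/32 fails and 64/64 passes. A 32/64 pair depends on the rule: the geometric mean is √(32 × 64) = 45.3, which passes; the lower value fails; the higher value passes. The protocol fixes none of these.

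**Lowest converting reading under 10.5.1.2 (single or concordant readings):**

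| Baseline reading | Rule | Lowest converting reading |
|---|---|---|
| <4 | ≥40 | 64 |
| 4 | ≥40 (below 8) | 64 |
| 8 | ≥4 × 8 = 32 | 32 |
| 16 | ≥4 × 16 = 64 | 64 |
| 32 | ≥4 × 32 = 128 | 128 |

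The requirement falls from 64 to 32 between baselines 4 and 8 and then rises again. A child going from 8 to 32 converts; a child going from 4 to 32 does not.

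**Source of the mismatch.** It lies in the definition: 4 × 8 = 32, not 40. On a continuous scale a baseline just under 8 would need 40 and a baseline of 8 would need 32. The grid only widens this to 64 against 32.

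**Baseline 4 has two readings.** Section 10.5.1.2 places it below 8 and calls it undetectable, so 64 is needed. Section 10.8.1.1 could be taken to treat it as measurable, so 4 × 4 = 16 would do.

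**Alternative series.** 10 × 2^k for k = 0 to 8 gives 10, 20, 40, 80, 160, 320, 640, 1280, 2560, again nine dilutions. With seronegative as below 10, a baseline <10 needs 40, a baseline of 10 needs 4 × 10 = 40, and a baseline of 20 needs 80. The two routes meet.

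**The case against.** **The series is provisional.** The laboratory is still to be chosen by tender and may agree deviations. That stands as a reason why correction is easy. It permits a correction but does not make one, and the protocol states both the series and the cut-off that does not fit it.

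**Every reading is classified.** A titre of 32 is below 40 and a titre of 64 is above it, so the label is not literally false. This stands too. The loss is in comparability with rates read on a series that contains 40.

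**Duplicates.** A reader might infer that every ≥40 rate will be a ≥64 rate. The documents do not support that, since some 32/64 pairs could pass. How duplicates are combined is normal content for a laboratory procedure or SAP, so its absence here is not a fault.

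**Power.** A reader might infer that the trial is underpowered. That would need 86.4% to have been measured at a true 40, plus a titre spread and a seronegative share that the protocol does not give. Assuming normal log2 titres with SD 1.5 to 2.5 and all children seronegative, power at 142 would be 64–70%. If the source studies effectively read 64 as well, nothing is lost. A range that wide, on inputs not in the documents, is no finding.

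**Bias between arms.** A reader might also infer this. All arms share one blinded assay and one grid, so the documents give no ground for it.

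**Conclusion.** The point holds in limited form. What is certain from the text is that none of the nine test dilutions is 40, and that a single or concordant reading passes only from 64. It is equally certain that the routes in 10.5.1.2 do not meet, because below 8 is paired with 40.

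The boundary fault reaches only children whose final reading falls where the routes disagree: under 10.5.1.2, a final 32 with a baseline below 8 (fails) or of 8 (passes). Under the alternative reading of 10.8.1.1, a baseline of 4 with a final 16 or 32 is also in doubt. How many children these are cannot be estimated from the protocol.

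The affected results are absolute seroconversion rates in seronegative children, seroprotection rates and the >70% check. Geometric mean titres do not use the cut-off. The non-inferiority comparison is not biased, and any effect on power depends on the unknown assay scale behind the 86.4%. It should be fixed, because it touches the definition of the primary variable and the correction is a text edit.

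**What to change.** Before the assays are run:

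- In 10.6.12.1, specify a two-fold series that contains 40, for example 10, 20, 40 … 2560. It keeps nine test dilutions and agrees with the synopsis, which lets the final dilution exceed 1:1024.
- Align the lines on the 1:4 enzyme treatment and the 1:4 and 1:8 serum controls with the new starting dilution.
- In 10.5.1.2, set the seronegative limit to below 10, and use the same wording in 10.8.1.1 so that a low baseline has one reading only.

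The cost is a few edited lines and the laboratory's agreement. The downside is that titres of 4 and 8 are no longer distinguished.

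If the 1:4 series is kept, label the reported rates with the threshold actually read. Restating the cut-off as 32 would also make the routes meet (baselines <4, 4 and 8 would all need 32). It gives up the ≥40 convention used throughout, so it is a trade-off rather than a plain correction. The rule for combining discordant duplicates can go in the laboratory procedure or the SAP.
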